## **8.3 Statistical Analyses and Sample Size**

The ITT will be used for testing the treatment efficacy based on patients who are SARS-CoVID-2 viremia negative at the baseline. The primary analysis will be to compare the rate of COVID-19 disease for each treatment group to the placebo group with a Mantel-Haenszel chi-square test with multiplicity adjustment using the Dunnett's step up method(11,12). The stratifying

variables will be those used for the randomization, site and High vs. Low risk groups. The high risk group include healthcare personnel (including environmental service) who work in COVID-19 care areas, emergency rooms and intensive care units caring for COVID-19 patients. First responders and DDOT bus drivers will be included as a high risk group. Low risk groups will include healthcare workers who work in non-COVID-19 care areas, without direct patient contact and those involved in administrative roles.

The DSMB chair will be provided with a weekly site SAE report to monitor safety. An interim analysis will be done when a half of patients have completed the 8 weeks assessments for an early treatment efficacy or a possible reassessment of study sample-size if the estimation of placebo rate is inadequate. Depending on response to the study intervention, the DSMB may decide it is necessary to stop/continue the trial if 1) there are safety concerns at any point in the trial or 2) there is evidence of treatment efficacy at the interim analysis; or recommendation for trial modification as it may be suggested, or 3) to continue the trial as designed. The DSMB will only stop the clinical trial for safety reasons.

Secondary analyses will be performed to evaluate the comparisons between the randomized arms and the chronic HCQ treatment comparator arm. Additional analyses will include assessments of inflammatory markers in both plasma and leukocytes, clinical characteristics associated with risk for COVID-19 acquisition, disease specific markers and clinical symptoms, as well as virologic markers and sequencing of positive COVID-19 patients during the study. Safety and AE reporting will also be done as part of the study. A detailed statistical analysis plan (SAP) will be written before the study is closed.

Sample size/power calculation:

With one planned interim analysis when 50% of the participants have completed their 8 week treatment and using an O'Brien-Fleming alpha spending method to ensure an overall type 1

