error of 0.05, the critical value for the interim analysis will be 0.0054 and the final critical value will be 0.0492. With a sample size of 900 per group and  $\alpha=0.0492$ , the power to detect a 32% reduction in COVID-19 disease rate (10% vs 6.8%) between the placebo group and each HCQ treated group would be 87%. Power calculations are also given for placebo rates of 8% and 15% with a 32% reduction in COVID-19 disease rates for the HCQ treated groups. Assuming 5-10% of patients will have SARS-CoVID-2 viremia positive at the baseline, we need 1000 per group with a total of 3000 patients to complete the trial.

Power calculations using simulations for Dunnett’s step up method

Assuming 900 per group and  $\alpha=0.0492$

COVID-19 disease rate in placebo	COVID-19 disease rate in treatment	Power
8%	5.4%	80%
10%	6.8%	87%
15%	10%	98%

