6.3.4. Proposed Analysis

6.3.4.1 General Statistical Consideration:

The statistical software package SAS® Version 9.4 or higher (SAS Institute, Cary, NC, USA) will be used to perform all analyses and to summarize data.

The analyses described in this statistical analysis plan (SAP) are considered a priori, in that they have been defined prior to database lock. Any analyses not described herein performed subsequent to database lock will be considered post hoc and exploratory.

6.3.4.2. Handling of missing data:

For summary statistics, results will be reported based upon observed data. The study will make all possible efforts to obtain patient's follow-up data and laboratory confirmation of infection for COVID 19 disease determination. The efficacy analysis will be performed based on all observed data assuming missing as random (MAR), two selected imputation approaches are specified for the sensitivity analysis.

6.3.4.3 Primary Efficacy Analysis.

The FAS is considered. Chi-square test will be used to compare the rate of COVID-19 disease in each randomized treatment group to that of the placebo group using Dunnett's step-up method to adjust for multiple comparisons and controlling for type I error^{1,2}. Specifically, Dunnett's step-up method uses a closed gatekeeping strategy, in which the largest p value will be evaluated first at critical value of 0.05; if that fails, the second p value will be evaluated at critical value of 0.0262 (details in the sample size /power calculation section). A treatment efficacy is detected if the largest p value <0.05 or the second p value <0.0262 . The results of

efficacy analysis will be validated through two specified imputation approaches described in below

Sensitivity Analysis #1: A Tipping Point Analysis (TPA) with delta-adjusting imputation

The primary analyses for COVID 19 disease is based on the observed data and the results are valid if the missing data are missing at random (MAR), meaning that the probability of a value being missing, conditional on the observed data and factors in the statistical model, is random and not dependent on the unknown value of the missing data point.

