6.4 Sample size/power calculation

Power Calculation for original Primary Aim: (based on original Study Protocol, dated 04/06/2020)

To determine if the use of hydroxychloroquine as preventive therapy decreases the rate of acquisition of SARS-CoV 2 infections in Study Participants as compared to placebo.

The sample size and power calculation for the original aim are based on a SARS-CoV 2 infection rate of 10% in the placebo-treated group, and an average of 6.8% in the randomized weekly- and daily- HCQ groups, with a relative reduction of 32%. Based on an alpha=0.05 two-sided test, with 900 subjects per group that are COVID negative at the baseline, and one interim analysis when 50% of participants (450 per group) have completed the study and primary

endpoint data assessment, we will have more than 80% power (82% to be exact using nQuery) to detect a significant HCQ effect if the observed test statistic is ± 2.9626 or $p\text{-value} < 0.003$ in the interim analysis, or ± 1.9685 or $p\text{-value} < 0.0497$ in the final analysis, using an O'Brien-Fleming alpha spending method to ensure an overall type 1 error of 0.05 and assuming that overall COVID positive rate in the weekly- and daily- dose HCQ groups is 6.8% with $n=1800$ in the HCQ treated group and 900 in the placebo treated group. A reduction of 36% can be detected between either one of the HCQ treatment groups and placebo, using the same assumptions. Assuming 5-10% of patients will have SARS-CoV 2 positive at the baseline, we need 1000 per group, with a total of 3000 participants to complete the trial.

Power Calculation for revised Primary Aim: (based on revised Study Protocol dated 04/16/2020 or after)

To determine if the use of hydroxychloroquine as preventive therapy decreases the rate of acquisition of SARS-CoV 2 infections with clinical COVID-19 disease in Study Participants for each randomized treatment arm as compared to placebo.

The revised sample size and power calculation are based on a 10% rate of clinical COVID-19 disease (with laboratory confirmation) in the placebo-treated group, and an average 6.8% rate in the two randomized HCQ-treated groups (weekly and daily dosing groups), with a relative reduction of 32%. We propose two looks; one look (interim analysis) when 50% of the participants have completed the study and primary endpoint assessment (for P1), and a final look when 100% of participants have completed the study.

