Based on an $\alpha=0.05$ two-sided test, chi-square test/logistic regression with odds ratio estimates, and Haybittle-Peto alpha spending method to ensure an overall type I error, the critical value for the interim analysis will be 0.001 and the critical value for the final analysis will be 0.05. For data illustration, we have also included an O'Brien-Fleming spending function approach for controlling type I error with a critical value of 0.0054 for the interim analysis and 0.0492 for the final analysis.

Power calculations are based on $n=900$ or 935 participants per study arm, using a simulation approach ($n=10,000$ simulations) in three correction methods: #1 comparing the weekly and daily HCQ dose arms to the placebo group separately using the Dunnett's step-up approach; #2 comparing the weekly and daily HCQ dose arms to placebo separately using a conservative Bonferroni approach with critical value of 0.025 for each test at the final look; #3 comparing the combined weekly and daily HCQ dose arms to the placebo using a single test.

With Haybittle-Peto boundary and $\alpha=0.05$ at the final look, the Dunnett's step-up correction uses a closed gatekeeping strategy for testing the daily dose arm vs placebo and the weekly dose arm vs placebo separately: the largest p value tested first will be at 0.05; if that fails, the second test will be at p value 0.026, delivered from the last row of Table 2 of Dunnett and Tamhane (1992), and validated based on simulation using R *DunnettTests* package. Likewise, at the interim look, the largest p value tested first will be at 0.001; if that fails, the second test will be at 0.0005.

Table 1. Power for different scenarios using varying methods. Sample size was determined using the Dunnett's Step up method with the Haybittle-Peto boundary.

Haybittle-Peto approach	$p_0=0.1, p_1=0.073, p_2=0.063$		$p_0=0.1, p_1=p_2=0.068$	
Method	n=900	n=935	n=900	n=935
#1 Dunnett's Step up	0.800	0.811	0.770	0.800
#2 Bonferroni	0.784	0.800	0.745	0.760
#3 Daily+weekly arms vs placebo	0.812	0.83	0.819	0.835

p_0 is the rate for the placebo treated group and p_1 and p_2 are the rates for the two treated groups.

O'Brien-Fleming approach	$p_0=0.1, p_1=0.073, p_2=0.063$		$p_0=0.1, p_1=p_2=0.068$		
Method	n=910	n=935	n=900	n=935	n=970
#1 Dunnett's Step up	0.8	0.814	0.76	0.776	0.801
#2 Bonferroni	0.787	0.8	0.741	0.761	0.784
#3 Daily+weekly arms vs placebo	0.815	0.83	0.815	0.83	0.846

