p_0 is the rate for the placebo treated group and p_1 and p_2 are the rates for the two treated groups.

For the primary Aim / hypothesis, we will use Dunnett's Step up approach to test each dose effect vs. placebo, and a sample size of 935 per arm will insure at least 80% power. The power will be higher for some of the secondary Aims (S1-S4 if use the compressed binary endpoint of infection presence or absence), since a single test will be used to study overall dose effect first, followed by subgroup analysis (Correction Method #3)

Assuming 5-10% of patients will be excluded from FAS, we need 1000 subjects per group, with a total of 3000 participants to complete the trial. The power and sample size calculation remained unchanged.

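### Protocol 8.3 states 87% power where SAP Table 1 gives 0.76 for the same sample size, rates and critical values, and the SAP's 80% claim fails at 10% exclusions if both HCQ arms are at 6.8%

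*Protocol*

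**What the plan says.** Protocol 8.3 plans a "Mantel-Haenszel chi-square test with multiplicity adjustment" by Dunnett's step-up method, stratified by site and risk group, with one O'Brien-Fleming interim look at 50% (critical values 0.0054 and 0.0492). With 900 per group and a 32% relative effect, its power statement reads: "reduction in COVID-19 disease rate (10% vs 6.8%) between the placebo group and each HCQ treated group would be 87" (percent). Its table, headed as a step-up simulation, gives 80%, 87% and 98% for 8% vs 5.4%, 10% vs 6.8% and 15% vs 10%. The protocol does not say whether the test is one- or two-sided.

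SAP 6.4 is based on a 10% placebo rate and "an average 6.8% rate in the two randomized HCQ-treated groups", and specifies a "two-sided test, chi-square test/logistic regression with odds ratio estimates". Its operative boundary is Haybittle-Peto (0.001/0.05). An O'Brien-Fleming version with the protocol's critical values is added as an illustration. The step-up rows of "Table 1. Power for different scenarios using varying methods" read:

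| Boundary | Arms 7.3% / 6.3% | Both arms 6.8% |
|---|---|---|
| Haybittle-Peto | 0.800 (n=900), 0.811 (n=935) | 0.770 (n=900), 0.800 (n=935) |
| O'Brien-Fleming | 0.8 (n=910), 0.814 (n=935) | 0.76 (n=900), 0.776 (n=935), 0.801 (n=970) |

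The SAP concludes that "a sample size of 935 per arm will insure at least 80% power", and then: "Assuming 5-10% of patients will be excluded from FAS, we need 1000 subjects per group". Its success rule (6.3.4.3) is met by either arm: "A treatment efficacy is detected if the largest p value <0.05 or the second p value <0.0262".

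**The concern.** The two documents give power figures 11 points apart for the same sample size, rates, multiplicity method and critical values. Read as power for at least one arm, the protocol puts the chance of missing the planned effect in both arms at 13%. The SAP's table puts it at 24% (23% under Haybittle-Peto). Read literally, as power for each arm, the protocol's 13% compares with about 35%. Either way, a null result would look more conclusive than the design allows. The planned interim reassessment of sample size would also start from the wrong baseline.

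The SAP's own 80% statement rests on 935 evaluable per arm, which its recruitment target does not secure across its stated 5-10% exclusion range.

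**Working it through.** **Inputs.** Sample sizes, rates and first-step critical values are from Protocol 8.3 and SAP 6.4; the look is at 50% of participants. The second-step Haybittle-Peto values (final 0.0262, interim 0.0005) are from SAP 6.3.4.3 and 6.7. The O'Brien-Fleming second-step values are not printed. They were derived for two arms sharing a control (correlation 0.5): two-sided 0.0258 final and 0.00275 interim; one-sided 0.0262 and 0.00277.

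**Method.** Three binomial arms were simulated, 400,000 runs per cell. Each HCQ arm is compared with placebo by the pooled chi-square statistic, z = (p0 − p1) / √[2p(1 − p)/n], where p is the pooled rate. At each look both arms are rejected if the larger p-value is below the first value; otherwise the arm with the smaller p-value is rejected if that is below the second. Power is the share of runs with at least one arm rejected at either look, unless stated.

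**Step 1: reproduce the SAP's O'Brien-Fleming cells.** Two-sided, both arms at 6.8%:

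| n per arm | Recomputed | SAP prints |
|---|---|---|
| 900 | 76.6% | 0.76 |
| 935 | 77.9% | 0.776 |
| 970 | 79.5% | 0.801 |

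The SAP cell that conflicts with the protocol is therefore sound.

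**Step 2: the protocol's table (n=900, 0.0054/0.0492).**

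| Placebo vs HCQ | Protocol states | Two-sided | One-sided |
|---|---|---|---|
| 8% vs 5.4% | 80% | 67.5% | 78.2% |
| 10% vs 6.8% | 87% | 76.6% | 85.3% |
| 15% vs 10% | 98% | 94.2% | 97.1% |

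No two-sided variant tried at n=900 comes near 87% under the step-up rule. Applying the thresholds one-sided comes within 2 points in each row, but always low.

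**Step 3: does the stratified test explain the gap?** A Mantel-Haenszel test over two risk strata was simulated (200,000 runs), assuming a high-risk share of 50-80% and a high-to-low rate ratio of 1 to 4. It gave 67.5-68.6 / 76.3-77.6 / 94.1-95.2%, a gain of about 1 point at most. Sites were not modelled.

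**Step 4: which power is it?** At n=900, 10% vs 6.8%, two-sided O'Brien-Fleming: at least one arm 76.6%, a given arm about 65.5%, both arms about 54.5%. Only the first matches the SAP table, so the protocol's wording about each arm does not describe the quantity tabulated.

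**Step 5: the exclusion allowance.**
- 1000 × 0.95 = 950; 1000 × 0.90 = 900.
- 935 survives only if exclusions are at most (1000 − 935)/1000 = 6.5%.
- Keeping 935 after 10% exclusion needs 935/0.90 = 1,039 per arm.

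Two-sided Haybittle-Peto power:

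| n per arm | Both arms 6.8% (printed) | Arms 7.3% / 6.3% (printed) |
|---|---|---|
| 900 | 76.3% (0.770) | 80.0% (0.800) |
| 935 | 78.2% (0.800) | 81.5% (0.811) |
| 950 | 78.8% (none) | 82.3% (none) |

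**Step 6: the 0.800 cell.** The standard error of a 10,000-run estimate near 0.78 is √(0.78 × 0.22 / 10,000) = 0.41 points. The gap of 80.0 − 78.2 = 1.8 points is about 4.4 standard errors; the other equal-arms step-up cells agree within about 1.6. The table hints at the same thing: from 900 to 935 power rises 1.6 points under O'Brien-Fleming (0.76 to 0.776) but 3.0 under Haybittle-Peto (0.770 to 0.800).

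**The case against.** Several points can fairly be made for the plan.

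- **The designs are not identical.** The protocol names a stratified test, the SAP a chi-square test or logistic regression. This is true, and the exact claim is the same sample size, rates, step-up method and critical values. Stratifying by risk adds about 1 point against a gap of about 10, so it does not explain the difference; strictly, site stratification was not checked.
- **The O'Brien-Fleming panel is only an illustration.** Also true, but the operative Haybittle-Peto cell is 0.770, which conflicts with 87% just as clearly.
- **The SAP supersedes the protocol figure.** It cites other protocol versions and a wider population, so the protocol at hand may be an earlier one. That limits the practical harm, but it does not give one set of inputs two powers, and the SAP closes by saying the calculation is unchanged.
- **The one-sided explanation is inference.** This stands. One-sided power at 950 per arm (80.2/86.9/97.7%) fits all three protocol rows better than at 900, so sidedness, sample size or both may be involved. The cause is not established.
- **The exclusion point is small.** On the SAP's figures it is 3 points, at the upper end of the range and in one of two scenarios. It should be read with that limit. Rechecking the 0.800 cell is likewise a 1.8-point matter.

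**Conclusion.** The concern holds. Protocol 8.3 overstates power relative to the SAP's two-sided test by about 12, 10 and 4 points in its three rows, and by 11 points against the SAP's printed 0.76. It also labels at-least-one-arm power as power for each arm, which is about 65%.

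The SAP's claim of at least 80% does not cover its own 5-10% exclusion range if both arms are at 6.8%: recomputed power is about 76-79% for 900 to 950 evaluable per arm. It does hold, at about 80-82%, if the arms are at 7.3% and 6.3%.

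The conflict between the documents, and 1000 less 10% being 900, need no modelling. The recomputed figures assume an unstratified pooled chi-square test, binomial outcomes, one look at 50% and the derived second-step O'Brien-Fleming values. The source of the protocol's 87% is not known. This should be fixed, but it does not call for a larger trial.

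**What to change.** **Protocol 8.3**
- State that the test is two-sided, as in the SAP, and name the boundary to which the power table refers. At 10% vs 6.8% and n=900 the choice barely matters (76.6% O'Brien-Fleming, 76.3% Haybittle-Peto).
- Replace 80/87/98% with about 67-68, 76-77 and 94%, labelled as power for at least one arm. These are approximate and unstratified; the sponsor should rerun the simulation with the planned stratified test and print its own figures and inputs.
- Reword the reference to each HCQ group as at least one HCQ group, or give the per-arm figure beside it (about 65% at n=900, 10% vs 6.8%).

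**SAP 6.4**
- Recheck the 0.800 cell (Haybittle-Peto, n=935, both arms 6.8%); it should be about 0.78.
- Replace the blanket 80% statement with power by scenario for 900 to 950 evaluable per arm: about 76-79% with both arms at 6.8%, and about 80-82% with arms at 7.3%/6.3%, each labelled as at least one arm.

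**Cost.** Wording in two documents and one simulation rerun. No extra patients are needed; the stated power becomes less favourable.

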## 9 PARTICIPANT INVOLVEMENT ENDPOINT/FOLLOW-UP

All Participants who sign the Consent and Authorization Form and provide three (3) blood sample draws, complete the baseline and week 1- 8 assessments, or after acquiring COVID-19 infection at any point during the study period are considered to have completed participation in this study. Participants will be followed for 30 days after meeting study endpoint for safety purposes. No further follow-up by the study Investigator is planned for Participants involved in this study thereafter. Electronic medical records will be accessed to obtain information on any diagnostic testing done for COVID-19 as part of the Participants’ routine care which may lead to diagnosis of COVID infection, including but not limited to PCR, serologies, rapid diagnostic tests, and other related tests.

## 10 SAFETY CONSIDERATIONS

### 10.1 Definitions of Adverse Events

An **Adverse Event (AE)** is any untoward medical occurrence in a Participant administered an investigational product or undergoing a procedure, which does not necessarily have a causal relationship with the treatment. An AE can be any unfavorable and unintended sign, symptom, or disease temporally associated with the use of an investigational product, whether or not it is related to the investigational product. *Development of COVID-19 disease will not be considered an adverse event as it is considered the study primary endpoint.*

A **Serious Adverse Events (SAE)** is any untoward medical occurrence that may present itself during a Subject's participation in a clinical trial that:

- Results in death,
- Is life-threatening,
- Requires inpatient hospitalization or prolongation of existing hospitalization,
- Results in persistent or significant disability/incapacity, or
- Is a congenital anomaly/birth defect.

Important medical events that may not result in death, be life threatening, or require hospitalization, may be considered a SAE when, based upon appropriate medical judgment, they may jeopardize the Participant and may require medical or surgical intervention to prevent one of the outcomes listed above. Medical care and hospitalization secondary to development of COVID-19 disease are considered study endpoints for this prevention study.

It should be noted that AEs that lead to hospitalization are considered SAEs. However, elective

hospital admissions not in response to an adverse event are not SAEs.

**Life-threatening** means that the Participant was, in the view of the PI, at immediate risk of death from the reaction as it occurred. This definition does not include a reaction that, had it occurred in a more serious form, might have caused death. Assessment of the cause of the event has no bearing on the assessment of the event's severity.

AEs will be considered to be **study-related** if the event follows a reasonable temporal sequence from a study-specific procedure and could readily have been produced by that study or medication procedure. Deaths, organ failures and other complications related to the Participants underlying conditions (including the disease or problem that caused the Participant to seek medical care), should **not** be considered study-related AEs.

## **10.2 Possible Risks & Benefits Associated with Study Procedures**

There is a potential health benefit to Participants by participating in this study, as the medication may help to prevent the acquisition or ameliorate the manifestations of COVID-19 infection. The COVID-19 testing results obtained from testing completed by the study investigators will be made available to the Participants when available to the investigator. If any Participant has a positive COVID-19 test during the study, the Participant will be referred to their respective healthcare provider for additional testing and treatment as recommended by the local guidelines. HFHS employees will be referred directly to employee health. First responders and DDOT bus drivers will be referred to their respective employee health services. Participants may also be referred to their primary care provider, if they choose so. Additional, secondary endpoint analyses and results will not be returned to the participating site and will not be used in the management of Participants. No personally identifiable testing for human

DNA will be performed on any samples obtained from this study. DNA testing on de-identified samples will be planned as a secondary study analyses to assess potential DNA markers of increased susceptibility to COVID-19 infection in our study population.

Hydroxychloroquine (HCQ) is considered a safe and effective drug in the treatment of Rheumatoid arthritis, Systemic Lupus Erythematosus and other autoimmune diseases, as well as for the prevention of Malaria infection (6). The 2015 American College of Rheumatology guidelines do not recommend any routine laboratory testing or electrocardiogram monitoring for patients taking HCQ standard doses (up to 400mg maintenance dose) daily (8). Side effects of the medication are varied including gastrointestinal symptoms, skin and hair changes, muscle pains, an irregular heartbeat, and others as listed in Pharmacy section 10.3, with most being mild and of unknown incidence. Severe but rare side effects include drug allergic reaction, cardiac arrhythmias with risk of death, hypoglycemia with concomitant hypoglycemic medications, visual changes, retinal disease and rarely blood cell count anomalies may occur. Participants with any potential medication associated drug-drug side effects and/or with any elevated risk factors associated with any significant HCQ side effects or toxicities, will be excluded from the study.

The only study-related procedure that could impact Participant safety is the collection of three (3) planned blood draws. The anticipated risks of collecting a blood sample specimen may include slight pain, discomfort, and/or the possibility of bleeding or bruising at the site.

Possible risk of loss of confidentiality could occur by obtaining study questionnaires and accessing the Participants' electronic medical records to determine assay results from any clinical testing for COVID-19 that may have been performed during their clinic or emergency room visit includes potential exposure of confidential medical information. Investigators will keep a separate patient key linking MRN to the study ID and will not provide this information to the study sponsor unless required by law. All study and clinical information will be kept in

secure electronic servers and in locked cabinets. Investigators will ensure that only the minimal amount of information needed for the study is accessed and recorded for study purposes. (See Confidentiality, section 11.3)

